### 5.1.2 Identification and recruitment of participants (MOPP Study)

The PROMPPT-FS Health Informatic Specialist will design a search and report compatible with the participating practice GP System of Choice (GPSoC), to identify eligible participants as outlined in section 4.3.2. The search and report will be provided to the practice, to screen their electronic patient records to systematically identify adults prescribed opioid-containing pain medicines for 6 months or longer (with a prescription dispensed in the last two months), and grouped according to the strength of opioid medicine (weak, intermediate, strong). Grouping will be based on a published categorisation for prescribed analgesics in primary care. GPs will be asked to screen the patients identified according to the study inclusion and exclusion criteria, excluding ineligible patients.

Each patient identified will be assigned an individual study ID and their details will be mail-merged into a Consent to Contact invitation pack (to include an Invitation letter, a Participant Information Leaflet (PIL), a Consent to Contact form and reply paid envelope) inviting them to receive further information about the MOPP study. The Consent to Contact invitation pack will be sent via Docmail from the practice. Docmail is a standards-compliant hybrid mail service, providing document management and ISO 27001 secure mailings. Non-identifiable

sample demographic data (including age and sex, and opioid strength grouping) will be provided to the research team. This will allow any evidence of selection bias to be assessed.

Response rates to mail-outs will be monitored and, if needed, a further Consent to Contact invitation pack will be sent from the practice to non-responders after 2 weeks.

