# Acceptability Questionnaire

Following the initial consultation with the practice clinical pharmacist, participants who gave consent to future contact about related studies, will be mailed a MOPP-2 recruitment pack by Keele CTU. The MOPP-2 Recruitment pack will include an invitation letter, Participant Information Leaflet, Acceptability Questionnaire (including consent form), an Interview Reply Slip and a prepaid envelope. Participants may choose to consent to any, all or none of these options.

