### 5.3.1 Self-reported questionnaires

All participants will be asked to complete self-report questionnaires at 2 time points:

- At baseline
- At 3 months from receipt of the completed baseline questionnaire.

Participants will return the questionnaires to Keele CTU in pre-paid envelopes. To maximise response rates to the questionnaires, participants will be sent a reminder postcard at 2 weeks and a reminder letter and further recruitment pack after 4 weeks.

The baseline questionnaire will collect information on participant characteristics (age, sex, and duration of pain) and will include the proposed primary and secondary outcome measures for a main cluster RCT, as described below.

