### Acceptability Questionnaire

All participants who attended the clinical pharmacist appointment will be mailed a short survey (known as the Acceptability Questionnaire) about their experiences of the consultation, which will supplement the qualitative data. This short survey will have a total of 12 questions from two existing measures: a modified version of the treatment acceptability and credibility measure and the Theoretical Framework of Acceptability (TFA) questionnaire. The modified acceptability and credibility measure has been used in previous similar studies. The measure includes 4 items, (scored on a 0-10 scale) and will assess (1) how logical the PROMPPT Intervention seems to participants, (2) how confident participants are that it will be successful in helping them (3) how confident participants would be in recommending it to a friend and (4) how satisfied they were with the intervention overall.

The TFA questionnaire comprises 8 items (scored on a 0-5 scale) . The first is a global acceptability question and the remaining 7 (items 2-8) represent key constructs of

acceptability relating to healthcare interventions (affective attitude, burden, intervention coherence, ethicality, perceived expectations, opportunity cost, and self-efficacy).

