# 6.5 Progression criteria

The findings will determine the extent of modification needed to the intervention, clinical pharmacist training and/or trial processes before proceeding to the main trial.

Criteria to progress to a main trial with no more than minor modifications are:

- Recruitment rate to MOPP: is ≥20% of eligible patients consent to participate
- >50% of MOPP participants attend at least one PROMPPT consultation
- ≥ 70% of MOPP participants complete 3-month follow-up questionnaires.
- Mean acceptability/credibility score (items 9-12 of the Acceptability Questionnaire) ≥ 5
- Evidence from interviews about intervention acceptability is in line with the TFA (e.g. PROMPPT is understandable/has coherence, is ethical, perceived as likely to achieve its purpose, does not place excess burden on participants and participants can and want to take part).

If these criteria are not met, discussions will follow in collaboration with the Programme Steering Committee to determine which elements of the intervention, training and/or trial processes need modification and these will be refined accordingly before proceeding to a main trial.

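### No reminder is described for the Acceptability Questionnaire, although its score is a progression criterion, reminders are written out for the other patient mailings, and two sections disagree on who is mailed it

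*Protocol*

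**What the plan says.** Protocol section 5.1.3 (Acceptability Questionnaire) says that, after the initial consultation, those who agreed to future contact "will be mailed a MOPP-2 recruitment pack by Keele CTU". The pack contains the questionnaire with its own consent form and an interview reply slip, and return is optional: "Participants may choose to consent to any, all or none of these options". Section 5.3.2 describes the same mailing with a different population: "All participants who attended the clinical pharmacist appointment will be mailed a short survey". Neither section says what happens if nothing comes back.

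Other patient requests have a written follow-up step:
- Consent to Contact pack (5.1.2): if needed, "a further Consent to Contact invitation pack will be sent from the practice to non-responders after 2 weeks".
- Recruitment pack with the baseline questionnaire (5.1.2): postcard at 2 weeks, then letter and second pack at 4 weeks.
- Baseline and 3-month questionnaires (5.3.1): "To maximise response rates to the questionnaires, participants will be sent a reminder postcard at 2 weeks", then a letter and pack at 4 weeks. That section covers two time points only, so it does not reach the Acceptability Questionnaire.
- Appointment booking (5.2): telephone reminders at 2 and 4 weeks.

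Section 6.5 lists "Mean acceptability/credibility score (items 9-12 of the Acceptability Questionnaire) ≥ 5" among five criteria for moving to the main trial with at most minor changes. No minimum return is attached. Section 6.2.8 sets the cut-off at 5 on the 0-10 scale and says the scores are read together with the qualitative data.

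**The concern.** The score is a mean among people who chose to return an optional survey about a consultation they had attended. Willingness to return it may be related to how they felt about the consultation. If so, the respondent mean differs from the mean of all attenders, and the gap grows as return falls. Of the patient questionnaires sent by post, this is the one with no described effort to raise return, yet it feeds a go/no-go cut-off.

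Reading the score beside the interviews is only a partial safeguard. Under 5.1.3 (Patient Interviews), interviewees are those who send back the reply slip from the same pack. A low return limits both sources at once, so agreement between them is weak evidence against selection.

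The two descriptions of who is mailed add a separate difficulty: a return rate cannot be read until it is clear whether the base is all attenders or only those who agreed to future contact.

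**Working it through.** **The protocol's own figures.** Section 6.1 states precision of about ±10% for a 75% follow-up rate in 80 participants: 1.96 × √(0.75 × 0.25 / 80) = 0.095, or ±9.5 points. It also states 47 recruits per practice: 270 × 0.70 × 0.25 = 47.25. Both reproduce. No return rate, sample size or precision is given for the Acceptability Questionnaire, so what follows is illustration.

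**How many questionnaires.** Inputs from the protocol: 80 participants (6.1) and the attendance criterion of more than 50% (6.5). At its edge, 80 × 0.50 = 40 attend. Assumed: the return rates, and an SD of 2.5 for the score. Half-width of the 95% interval = 1.96 × 2.5 / √n.

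| Return (assumed) | Returned of 40 | Half-width |
|---|---|---|
| 40% | 16 | 1.2 |
| 60% | 24 | 1.0 |
| 75% | 30 | 0.9 |
| 90% | 36 | 0.8 |

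Under the 5.1.3 population, if 80% agreed to future contact (assumed), 40 × 0.80 = 32 are mailed. Returns of 40% to 90% then give 32 × 0.40 = 12.8 to 32 × 0.90 = 28.8, about 13 to 29.

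**How sensitive the cut-off is.** With return rate r and respondent mean m, the mean over everyone mailed equals 5 when non-respondents average (5 − r·m)/(1 − r). Example: r = 0.5, m = 6 gives (5 − 3)/0.5 = 4.0. Both r and m are assumed.

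| Return r | m = 6 | m = 5.5 |
|---|---|---|
| 40% | 4.3 | 4.7 |
| 50% | 4.0 | 4.5 |
| 60% | 3.5 | 4.25 |
| 75% | 2.0 | 3.5 |
| 90% | not possible (−4.0) | 0.5 |

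At 40% to 50% return, a modest difference between respondents and non-respondents would carry the overall mean to the cut-off. At 75% the difference has to be much larger (4 points when m = 6). At 90% it is out of range for m = 6 and nearly so for m = 5.5. The same algebra works the other way if dissatisfied patients reply more readily: a respondent mean below 5 could then hide an overall mean above it.

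**The case against.** The strongest reply is that silence is not a rule. A reader might infer that the questionnaire is mailed once and that non-responders are left alone. The protocol says neither; it describes a mailing and stops, and reminders could still be sent. That stands, so the point is that no reminder is described.

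A reader might also infer that the score comes from easily reached, satisfied patients and is inflated. The document does not support that. Everyone mailed has already returned a baseline questionnaire and attended a consultation, and dissatisfied patients may be the keener to answer. Nor does anything in the protocol show how far reminders would raise return.

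It would be too strong, too, to say this score decides progression. It is one of five criteria, it is integrated with uptake, attendance and process-evaluation findings (6.4), and a missed criterion leads to discussion with the Programme Steering Committee. That safeguard, however, is triggered only by a miss, so it would not catch a mean that passes because of who replied.

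A lighter approach for an optional sub-study is a defensible choice, but the protocol does not present it as one. Finally, reporting the return rate is something an analysis plan or the study report could supply, and section 3 already lists responses to this questionnaire as an outcome. Its absence alone is not a fault. Reminders differ: they are contacts with participants, which this protocol specifies elsewhere and an analysis plan cannot add.

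**Conclusion.** The point holds as a cheap improvement, together with one inconsistency to reconcile. The protocol describes no reminder for the questionnaire behind a progression criterion while describing one for the other patient mailings and for booking. The interview reply slip shares the pack, so non-response would affect both patient sources on acceptability. Sections 5.1.3 and 5.3.2 contradict each other on who is mailed.

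Neither the size nor the direction of any bias can be derived. The illustrative figures rest on assumed attendance at the 50% edge, assumed returns of 40% to 90%, respondent means of 5.5 and 6, and an SD of 2.5. They show only that the cut-off can be sensitive to non-response at low return and becomes much less so as return rises.

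**What to change.** 1. In 5.1.3, send non-responders to the MOPP-2 pack the reminders already used for the other questionnaires: a postcard at 2 weeks and a letter with a further copy at 4 weeks. Time these to avoid the 3-month questionnaire, which runs from receipt of the baseline questionnaire. For example, if the pack went out 9 weeks after baseline receipt (assumed), the second reminder would fall at 9 + 4 = 13 weeks, about when the 3-month questionnaire is due.
2. Reconcile 5.1.3 with 5.3.2 so that one population is mailed and the denominator is defined.
3. In 6.2.8 and 6.5, give the number returned out of those mailed, and out of all attenders, beside the mean.

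The cost is a small protocol amendment, postage, and up to two extra contacts per non-responder. With 40 mailed and 50% return (assumed), that is at most 20 × 2 = 40 mailings. The extra contacts are a real, if small, burden, because participants may already receive reminders for the baseline pack, booking and the 3-month questionnaire. Returns not sought during the study are hard to recover afterwards.

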#### Patient Interviews

Patient participants who return the Interview Reply Slip consenting to further contact for an interview, will be contacted by a researcher to arrange a mutually convenient time and location for this. Interviews may be conducted face-to-face or by telephone. Face-to-face interviews are likely to take place in the participants' own home. When interviews take place in a person's home, they will be conducted in accordance to Keele University's lone working guidelines. The qualitative researcher(s) and a nominated contact will follow standard procedures regarding contact before and after the interview.

An interview confirmation letter will be sent specifying the date, time and location (or telephone number). A letter will be sent to the participant's GPs informing them that their patient is taking part in an interview. Once the target sample size of 15 participants has been reached, all subsequent participants who return their interview reply form will be sent a letter thanking them for their interest and informing them that we will not be inviting them to take part on this occasion.

Fully informed consent will be obtained prior to all interviews commencing.

For telephone interviews, the researcher will read through and complete the consent form with the participant over the phone; this will be undertaken verbally and recorded prior to the interview commencing. The participant will then send back a signed consent form on completion of the interview.

#### Clinician Interviews

Clinical pharmacists and GPs who consent to being interviewed will be contacted by a researcher, after the majority of initial reviews in their practice have been completed, to schedule a mutually convenient appointment. The interviews may be conducted face-to-face or by telephone. Face-to-face interviews will be arranged at a location convenient for the interviewee, likely to be their clinical practice setting. An interview confirmation letter will be sent to the clinician specifying the date, time and location (or telephone number) of the interview.

Fully informed consent will be obtained prior to all interviews commencing.

For telephone interviews, the researcher will read through and complete the consent form with the participant over the phone; this will be undertaken verbally and recorded prior to the interview commencing. The participant will then send back a signed consent form on completion of the interview.

### 5.2 PROMPPT Intervention

Following receipt of a completed baseline questionnaire, MOPP participants will be mailed an invitation letter (GP headed paper) asking them to schedule, at their earliest convenience, a pain review with the clinical pharmacist working at their practice. Telephone reminders will be made by the practice after 2 weeks and 4 weeks if appointments have not been arranged.

Patients who do not have a pain review with the clinical pharmacist will continue with usual GP care.

#### 5.3 Outcome data collection

This feasibility study will report on both process and research outcomes and data will be collected via participant self-reported questionnaires, clinical pharmacist-completed CRFs, audio-recordings of the PROMPPT consultations and semi-structured interviews with patients and clinicians. These methods of data collection will enable the acceptability and feasibility of training the clinical pharmacists delivering the PROMPPT intervention and delivering a larger randomised cluster RCT to be fully assessed. Table 1 (below) summarises the outcome measures and their respective time-points of data collection.

### 5.3.1 Self-reported questionnaires

All participants will be asked to complete self-report questionnaires at 2 time points:

- At baseline
- At 3 months from receipt of the completed baseline questionnaire.

Participants will return the questionnaires to Keele CTU in pre-paid envelopes. To maximise response rates to the questionnaires, participants will be sent a reminder postcard at 2 weeks and a reminder letter and further recruitment pack after 4 weeks.

The baseline questionnaire will collect information on participant characteristics (age, sex, and duration of pain) and will include the proposed primary and secondary outcome measures for a main cluster RCT, as described below.

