On receipt of a Consent to Contact invitation pack, the potential participant will complete the Consent to Contact form and return this in the pre-paid envelope provide to Keele Clinical Trials Unit (CTU), Keele University. Consent for Keele CTU to contact the potential participant providing them with further information regarding the MOPP Study will be obtained, in line with the definition outlined in Article 4(11) of the GDPR guidance, "any freely given, specific, informed and unambiguous indication of the data subject's wishes by which he or she, by a statement or by a clear affirmative action, signifies agreement to the processing of personal data relating to him or her" (European Union, 2016). Consent to be contacted with a MOPP Study invitation pack will therefore be implied by return of a completed Consent to Contact form.

On receipt of a completed Consent to Contact form, Keele CTU will mail potential participants a MOPP Study recruitment pack (to include; an invitation letter, Patient Information Leaflet, Baseline Questionnaire including consent form, and a prepaid envelope). A reminder postcard will be sent to non-responders after 2 weeks. A further reminder letter & recruitment pack will be mailed to non-responders after 4 weeks. A letter will be sent to participants where data is missing from consent forms in order to check that they are happy to take part in the study and that all required information is collected.

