#### 6 STATISTICS AND DATA ANALYSIS

# 6.1. Sample size

Based on data from our regional anonymised primary care database (Consultations in Primary Care Archive (CiPCA)), we expect to identify around 270 patients with persistent pain prescribed long-term opioids per average sized practice of around 5000-6000 patients. Assuming GPs exclude 30% of patients identified according to study exclusion criteria and assuming that a minimum of 25% of those contacted consent to participate and return a baseline questionnaire, we estimate a mean of at least 47 eligible patients per practice will consent to participate.

A sample of 80 eligible participants from across 4 practices in 2 regional centres is therefore feasible and will allow us to estimate the overall consent rate with precision of at least  $\pm 10\%$ . Similarly, if the 3-month follow-up rate is around 75%, this estimate will have precision of around  $\pm 10\%$ .

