#### 6.2.6 Health economic evaluation

A formal health economic evaluation will not be conducted in this feasibility study.

To assess the feasibility of the proposed health economic evaluation for the main trial, we will assess the level of completion of the EQ-5D-5L questionnaire at baseline and 3 months, and the level of completion and suitability of the patient resource use questionnaire at 3 months.

Overall response rates for each questionnaire will be calculated. Within questionnaire completion rates will also be calculated in order to assess the level of completion of specific questions. Assessment of appropriateness of completion will also be undertaken, with questions to be refined as necessary.

Data on opioid prescriptions and use will be available from patient self-report questionnaires and medical record review. This will allow comparison of the two data sources to determine the final method of data collection on opioids for the economic evaluation within the definitive trial.

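### The only reminder text covering the 3-month questionnaire sends a recruitment pack, which holds the baseline questionnaire and consent form instead of the follow-up questionnaire

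*Protocol*

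**What the plan says.** Section 5.3.1 opens with "All participants will be asked to complete self-report questionnaires at 2 time points", which it lists as baseline and 3 months after receipt of the completed baseline questionnaire. It then gives a single reminder procedure, aimed at raising response to the questionnaires in general: "participants will be sent a reminder postcard at 2 weeks and a reminder letter and further recruitment pack after 4 weeks". It has no separate wording for the 3-month questionnaire.

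Section 5.1.2 defines the MOPP Study recruitment pack as "an invitation letter, Patient Information Leaflet, Baseline Questionnaire including consent form, and a prepaid envelope". It also sets the reminders at recruitment: a postcard after 2 weeks, and then "A further reminder letter & recruitment pack will be mailed to non-responders after 4 weeks".

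The 3-month return is used in three places:

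- Section 6.2.1 estimates the proportion returning the 3-month questionnaire, out of those who consented to questionnaires at baseline.
- Section 6.5 makes it a progression criterion: at least "70% of MOPP participants complete 3-month follow-up questionnaires".
- Section 6.2.6 uses it to assess "the level of completion and suitability of the patient resource use questionnaire at 3 months", which serves primary objective 5.

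No section describes a 3-month follow-up pack or any other reminder for that time point.

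**The concern.** The reminder in 5.3.1 names a mailing that cannot do its job at 3 months. Someone due a 3-month questionnaire has, by definition, already returned the baseline questionnaire and the consent form inside it. Sending the recruitment pack again would invite that person to join a study they are already in, ask for consent a second time, and leave out the document that is overdue.

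Two things would be at stake if the text were applied literally. First, some 3-month returns that a second copy would have brought in could be lost, and these count towards the retention criterion. Second, a participant might fill in and return the enclosed baseline form. That form would not carry the resource-use items that 6.2.6 assesses at 3 months, and the protocol does not say whether it would count as a completed follow-up.

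**Working it through.** **Step 1. What does the 5.3.1 sentence add?** Section 5.1.2 already gives the baseline reminders in full: a postcard at 2 weeks, then a letter and recruitment pack at 4 weeks. Consent is given by returning the baseline questionnaire with its consent form (section 5.1.2, under the heading on consent to participate). For baseline, then, the 5.3.1 sentence repeats 5.1.2. What it adds is the 3-month reminder, and there it names the wrong pack.

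**Step 2. Do the two instruments differ?** Section 6.2.6 assesses EQ-5D-5L completion at baseline and 3 months, but resource use at 3 months only. In Table 1 the resource-use and work rows each carry one mark, in the 3-month column. The table is broken in the text available, and the demographics row shows the same pattern although 5.3.1 collects age and sex at baseline. I therefore rest this step on 6.2.6. By 5.3.1 the baseline form does carry the proposed primary and secondary outcome measures for the main trial, so a baseline form returned at 3 months would not be empty. What it would lack is the resource-use section.

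**Step 3. Reproduce the plan's figure.** Section 6.1 plans for 80 participants and states that "if the 3-month follow-up rate is around 75%, this estimate will have precision of around" ±10%. The 95% half-width is 1.96 × √(0.75 × 0.25 / 80) = 0.095, or 9.5 points, which agrees. No stated number is wrong.

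**Step 4. The margin.** Expected returns are 0.75 × 80 = 60. Returns needed are 0.70 × 80 = 56. The margin is 4 questionnaires.

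**Step 5. How much could the wrong pack matter?** Let s be the share of the expected returns that depend on the 4-week mailing. The protocol does not give s, so the range below is an assumption. Suppose also, as the worst case, that every such return is lost. The return rate is then p = 0.75 × (1 − s). With X ~ Binomial(80, p), treating participants as independent, the chance of meeting the criterion is P(X ≥ 56).

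| s (assumed) | p | Expected returns of 80 | P(X ≥ 56) |
|---|---|---|---|
| 0% | 75.0% | 60 | 0.88 |
| 5% | 71.3% | 57 | 0.65 |
| 6.7% | 70.0% | 56 | 0.56 |
| 10% | 67.5% | 54 | 0.37 |
| 20% | 60.0% | 48 | 0.04 |

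The result runs from no effect to a large one and depends wholly on s. The table shows that the margin is thin. It does not predict what will happen.

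**The case against.** The strongest reply is that this is carried-over wording and not a chosen procedure. The 5.3.1 sentence nearly repeats the recruitment reminder in 5.1.2, and its stated aim of raising response makes sense only if the overdue questionnaire is sent. Trial staff may well send the right form whatever the text says. The first 3-month mailing and the 2-week postcard are unaffected in any case. This stands as an explanation and keeps the point minor. It does not remove the point, because the protocol contains no other 3-month reminder text to follow.

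A reader might infer that the retention criterion would fail. The documents do not support that. Failure needs more than 4 of the expected 60 returns to depend on the 4-week mailing and be lost, and no figure for that share is given.

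A reader might also infer that this wording could by itself stop progression. Under section 6.5 the criteria govern progression with no more than minor modifications. Missing one leads to discussion with the Programme Steering Committee about what needs changing, and a faulty reminder could be found and corrected then. The Study Management Group also monitors follow-up procedures during the study (sections 8.1 and 9.5).

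Nor is all 3-month information at risk. A returned baseline form would still hold the proposed co-primary outcomes, and section 6.2.5 also takes morphine equivalent dose from medical records. The exposed items are those for objective 5, together with the unsettled question of whether such a form counts as follow-up.

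**Conclusion.** The inconsistency between 5.3.1 and 5.1.2 is real, and the rule is wrong as written for the 3-month time point. Applied literally, it sends people who have already consented a baseline questionnaire and consent form, with no second copy of the follow-up questionnaire.

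The possible effects are fewer 3-month returns against a planned margin of 4 in 80, and gaps in the resource-use data for objective 5. The size of either effect cannot be stated from the protocol. It depends on whether staff follow the text literally and on how many returns the 4-week mailing would bring, and neither is known. No sample size, precision figure or threshold is affected. Severity is minor: a wording error in an operative instruction, worth correcting because retention is one of the things the study sets out to measure.

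**What to change.** In section 5.3.1, separate the two time points. For baseline, refer to the reminders in 5.1.2. For 3 months, keep the postcard at 2 weeks and state that the 4-week reminder letter encloses a further copy of the 3-month follow-up questionnaire, without recruitment or consent material. Check that the mailing template matches.

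The cost is a sentence or two of protocol wording and a template check. The sample size, the analysis and the progression criteria stay as they are.
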